## 5.3 FORMAL STATISTICAL ANALYSES

### 5.3.1 Outcomes for all analyses

#### Primary outcome:

30-day mortality following PICU admission (following first admission) using data from the Office of National Statistics.

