#### **Admitted Patient Care (APC) and Emergency Department Dataset (EDDS), NHS Wales: linkage undertaken by NHS Wales Informatics Service**

The ethical approval and CAG approval to access the Welsh data have not yet been acquired (as at May 2018). When these have been obtained, data will be applied for. NHS Wales will only undertake linkage using NHS Number.

FLOW OF DATA IN THE DATA LINKAGE PART OF THE DEPICT STUDY

The DEPICT study, IRAS ID 218569

07/07/2017

Red boxes indicate transfers where personal data will be included; blue boxes indicate no personal data will be included in the transfer. All transfers will utilise secure transmission means.

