## 4 DATA & DATA MANIPULATION

---

The data acquisition will follow these steps as outlined in the NHS Digital application:

- 1) Data flows to NHS Digital from the University of Leeds (PICANet) and ICNARC (Case Mix Programme) will each securely transfer a file to the NHS Digital Data Access Request Service (DARS). These files will contain person-identifiable information (NHS Number, sex, post code, date of birth) and unique study identifiers (PICANet: DEPICT Study Number; CMP: CMP identifier) required to perform the data linkage.
- 2) NHS Digital will identify common records between PICANet data and CMP data.
- 3) Data flow from NHS Digital will return linked HES and ONS mortality data for all individuals in the PICANet or ICNARC datasets to the University of Leicester - NHS Digital will supply a list of the study identifiers common to PICANet and CMP to University of Leicester - The unique study identifiers (DEPICT study number and CMP identifier) will be appended to the end of every episode record returned to the University of Leicester.
- 4) The team at the University of Leicester will securely transfer the list of DEPICT study numbers and CMP study identifiers to University of Leeds and ICNARC respectively. No HES or ONS data or personal identifiers will be transferred.
- 5) Data flow from University of Leeds (PICANet) and ICNARC (CMP) University of Leeds and ICNARC will provide admission level clinical data from their respective audits for the specific DEPICT and CMP identifiers to University of Leicester by means of secure transfer. No personal identifiers will be transferred.

Data acquisition from NHS Wales will follow a similar process and data flow.

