### 4.1 INCLUSION/EXCLUSION

Data on all children ( $\leq 16$  years old) admitted to PICUs in the England and Wales from 2014 to 2016 following transport by a specialist team will be included. Transport events will be linked with the appropriate admission information and other longer-term outcome data. Some children will be transported and admitted more than once over this time period. Summary statistics will be produced for both admission and for the individual child, and analyses will be undertaken using both approaches and compared. For the analysis at child level, the admission closest to the final event will be used and a variable will be included to indicate if they had previous admissions to PICU.

Exclusions will be made for:

- Transport of adults (age  $>16$  years)
- Transport to an unknown location; no match between transport and admission event; transport performed by non-specialist team; transport performed by neonatal team.

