#### Secondary outcomes to include:

a) Mortality at fixed time-points (PICU discharge, 90 days and 1 year following [first] PICU admission – data linked from ONS)

b) Number of PICU admissions during study period and time to readmission (if applicable)

- c) Length of stay in PICU (number of days from PICU admission to discharge, for each PICU admission)
- d) Resource use in PICU (number of days of invasive ventilation, vasoactive agent therapy, renal replacement therapy and extra-corporeal life support during PICU stay, for each PICU admission)
- e) Length of hospital stay linked to the first PICU admission (number of days from hospital admission to hospital discharge)
- f) Number of A&E attendances in the 12 months following discharge from the first PICU admission (using data from HES and NHS Wales)
- g) Hospital resource use (total number of days admitted to hospital) in the 12 months following discharge from the first PICU admission (using data from HES and NHS Wales)

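### Mortality is sourced from ONS alone with no rule for children who cannot be traced, so a death that PICANet recorded may be missed

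*SAP*

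**What the plan says.** - **Primary outcome (SAP 5.3.1):** "30-day mortality following PICU admission (following first admission) using data from the Office of National Statistics". No second source is named.
- **Secondary outcome, item a (SAP 5.3.1):** "Mortality at fixed time-points (PICU discharge, 90 days and 1 year following [first] PICU admission", followed within the same bracket by "data linked from ONS".
- **Eligibility (SAP 4.1):** all children "admitted to PICUs in the England and Wales from 2014 to 2016 following transport by a specialist team will be included". The exclusions that concern matching or team type are "no match between transport and admission event; transport performed by non-specialist team; transport performed by neonatal team". A failed ONS, HES or NHS Wales trace is not among them.
- **Data flow (SAP 4, step 3):** NHS Digital "will return linked HES and ONS mortality data for all individuals in the PICANet or ICNARC datasets". Nothing is said about individuals for whom no trace succeeds, or about a flag that would identify them.
- **ONS content (SAP 3.3):** the data come from death certificates. If full ONS data are refused, the fallback is derived mortality at 30 days, 90 days and 1 year.
- **Welsh hospital data (SAP 3.3):** "NHS Wales will only undertake linkage using NHS Number".
- **Other mortality information:** SAP 4.2 takes its 7% 30-day mortality from PICANet data, SAP 3.2 requests vital status at discharge from ICNARC, and SAP 5.2 lists deaths in PICU as a summary item without naming a source.

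**The concern.** A death register returns something only for a death. Without a separate statement that a child was traced, an empty ONS result has two meanings: alive, or not found. The plan gives no rule for telling them apart and does not say that a death in the audit record counts when ONS returns nothing. The natural default in coding is to score the empty result as alive.

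Two things are at stake. First, the mortality rate could be understated. Second, if the chance of being traced differs by transport service or response time, the error is not balanced across the exposure and the odds ratio in Model 1 is biased. Items f and g (A&E attendances and hospital days in the following 12 months) have the same weakness: no linked record looks like no use, and a count model will accept the zero as genuine.

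**Working it through.** **Inputs from SAP 4.2:** 15,000 transports; 85% reached within 3 hours; 30-day mortality 7%; target contrast 7% v 4%. **Assumed:** the untraced share u (the SAP gives none) and two-sided alpha 0.05 (alpha is not stated; SAP 5.3.6 specifies 95% intervals).

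**1. The plan's own figures.** 15,000 × 0.85 = 12,750 and 15,000 × 0.15 = 2,250, as stated. Power for 7% v 4% with these groups is 99.99%, so the claim of adequate power holds. Expected deaths are 15,000 × 0.07 = 1,050, treating each transport as a separate child, as SAP 4.2 does.

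**2. Deaths lost if untraced children were scored alive.** Deaths lost = 1,050 × u; observed mortality = 7% × (1 − u).

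| u (assumed) | Deaths lost | Observed mortality |
|---|---|---|
| 1% | 10.5 | 6.93% |
| 2% | 21 | 6.86% |
| 5% | 52.5 | 6.65% |
| 10% | 105 | 6.30% |

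Power for the target contrast stays above 99.9% throughout. This is a misclassification problem, not a power problem.

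**3. Equal tracing in both groups.** With 7% late and 4% early, the true odds ratio is (0.07/0.93)/(0.04/0.96) = 1.81. At u = 5% in both it is (0.0665/0.9335)/(0.038/0.962) = 1.80. The effect is negligible.

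**4. Unequal tracing, true odds ratio 1.00 (7% in both groups).** Observed OR = odds[0.07(1 − u_late)] / odds[0.07(1 − u_early)].

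| u late | u early | Observed OR |
|---|---|---|
| 5% | 2% | 0.97 |
| 6% | 2% | 0.96 |
| 10% | 3% | 0.92 |
| 10% | 2% | 0.91 |
| 2% | 10% | 1.10 |

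For example, 6% v 2%: (0.0658/0.9342)/(0.0686/0.9314) = 0.96.

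**5. Effect of an either-source rule.** If a share s of 30-day deaths occurs in PICU, the loss falls from 1,050 × u to 1,050 × u × (1 − s). The SAP does not give s. Over its whole range from 0 to 1, the rule leaves the loss unchanged at worst and removes it at best.

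**6. A trap in the repair.** Suppose untraced children are removed but those who died in PICU are kept. If all 30-day deaths occur in PICU, the odds in each group become 0.07/[0.93 × (1 − u)]. A true odds ratio of 1.00 then reads (1 − 0.02)/(1 − 0.06) = 0.98/0.94 = 1.04 at 6% late v 2% early. That is about as large as the bias being corrected.

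**7. Would the missing-data rule catch it?** SAP 5.1 acts when a key variable has 10% or more missing values. An untraced child coded as no death has no missing value, so the rule would not be triggered. Even if trace failure were coded as missing, shares below 10% would stay under the threshold.

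**The case against.** The strongest reply is that the SAP nowhere says untraced children are alive. A reader might infer that they are all counted as survivors and that a PICU death known to PICANet is overridden. The text does not support that. Two other readings are open: their outcome could be set to missing under SAP 5.1, or they could drop out at step 5 of SAP 4, where the audits send clinical data only for listed identifiers. This stands, and the point is worded accordingly. It does not remove the gap: the three readings give different denominators and the SAP chooses none.

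Other replies, and what remains of them:

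- *The ONS label in item a may not govern PICU discharge.* The fallback in SAP 3.3 omits that time point, which suggests another source. This is possible, but none is named, and under the fallback the ONS route would supply no PICU-discharge outcome at all.
- *The link to ONS uses four identifiers (NHS number, sex, postcode, date of birth).* Correct: a missing NHS number does not by itself make a child untraceable for deaths. The NHS-Number-only rule concerns Welsh hospital data and bears on items f and g only; it is not evidence that Welsh deaths are under-traced. Nor does the listing of private units in SAP 3.1 say anything about tracing.
- *Missing-data handling goes to the Study Management Group before analysis, and SAP 5.3.5 requires sensitivity analyses on missing-data assumptions.* Both are useful, but generic; neither mentions linkage failure.
- *The bias is hypothetical and small.* The shares are assumptions and the direction can reverse. Odds ratios are reported to one decimal, so 0.96 would print as 1.0. A random effect for transport team would absorb part of any between-service difference in tracing; the alternative that SAP 5.3.3 allows, robust standard errors, would leave the coefficient as it is.

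**Conclusion.** The point holds as a gap in the outcome definition, not as a demonstrated bias. ONS is the only named source for the primary outcome, eligibility does not require a trace, and no rule or flag separates untraced from alive. Deaths recorded by PICANet may therefore be missed, and unlinked children may read as zero in items f and g.

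The size is unknown. The illustrative range (10.5 to 105 deaths lost; a true odds ratio of 1.00 read as anything from 0.91 to 1.10) rests on assumed untraced shares of 1% to 10%, on untraced children being scored alive, and on tracing being unrelated to death within each group. That tracing differs by service or response time is plausible but not shown in the SAP. If it does not differ, the odds ratio is essentially unaffected and only the rate is understated. The change is still worth making: an either-source rule can only recover real deaths, and it uses audit data that the study is already due to receive.

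**What to change.** - **Primary outcome:** count a death dated within 30 days of PICU admission in either PICANet or ONS.
- **PICU-discharge mortality:** take it from PICANet for all children and separate it from the ONS label in item a.
- **Trace status:** request a flag from NHS Digital and NHS Wales. Treat post-discharge outcomes, including items f and g, of untraced children discharged alive as missing, not as alive or zero. Handle these missing values explicitly (SAP 5.1 already considers multiple imputation), whatever their percentage; do not drop these children while keeping untraced deaths.
- **Sensitivity analyses:** (i) exclude all untraced children, including those who died in PICU; (ii) count all untraced PICU survivors as alive. Never add back untraced deaths alone, for the reason in step 6 of the working.
- **Reporting:** tabulate untraced children by transport service and exposure group.

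The cost is revised wording, one flag to request from the linkage bodies, one extra table, and a small loss of untraced children from the post-discharge outcomes.

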#### Secondary outcomes to include:

a) Mortality at fixed time-points (PICU discharge, 90 days and 1 year following [first] PICU admission – data linked from ONS)

b) Number of PICU admissions during study period and time to readmission (if applicable)

- c) Length of stay in PICU (number of days from PICU admission to discharge, for each PICU admission)
- d) Resource use in PICU (number of days of invasive ventilation, vasoactive agent therapy, renal replacement therapy and extra-corporeal life support during PICU stay, for each PICU admission)
- e) Length of hospital stay linked to the first PICU admission (number of days from hospital admission to hospital discharge)
- f) Number of A&E attendances in the 12 months following discharge from the first PICU admission (using data from HES and NHS Wales)
- g) Hospital resource use (total number of days admitted to hospital) in the 12 months following discharge from the first PICU admission (using data from HES and NHS Wales)

### 5.3.2 Model development

Model development will follow these steps:

1. Selection of key confounders to be included in analyses. Potential confounders and adjustments are included in the below table. Discussion will be led by clinical colleagues and facilitated by the statistician who will provide information about data available via the linked datasets and also provide details about data quality and potential issues with the data (see Section 5.1).
2. Directed Acyclic Graphs (DAG) will be produced following discussions to visually represent the potential adjustments for each model. The DAG will be approved by clinical colleagues involved in this study. This discussion will initially focus on Model 1 with the key outcome of 30-day mortality.
3. Formal model will then be fitted (see Section **Error! Reference source not found.**)
4. Model checking will be conducted (see Section 5.3.4)
5. Sensitivity analyses on assumptions and robustness of results will be conducted (see Section 5.3.5).

The DAG developed for each research question will be approved by the Study Management Group before analysis begins and it will be published in any paper presenting the results. Each model will have a different DAG. Use of a DAG will allow us to minimise the number of adjustments required. DAGitty (<http://www.dagitty.net/>) will be used to facilitate the drawing of the DAG and selecting the minimal model required.

#### **Potential variables for inclusion in analyses**

For our first model which will investigate the issues of timeliness of access to care, there are three time scales which can be defined as 'timeliness' (our exposure of interest):

- Time to arrival at bedside after acceptance (we will investigate this first)
- Time of referral to time of acceptance
- Time of referral to time of admission to PICU

For each of these time scales there are different factors which will be important. For example, care provided by the retrieval team upon arrival will impact on the time to

admission in the PICU but not the other time scales. This table provides a pool of variables which we will select from.

**List of potential confounders for consideration in each of the models.**

Variable	Data source
Age	PICANet & CMP
Sex	PICANet & CMP
Ethnicity	HES
Pre-existing comorbidities (or a proxy, e.g. time in hospital in the previous year)	HES, PICANet & CMP
Deprivation (IMD score)	PICANet & CMP (via postcodes)
Diagnosis	PICANet/CMP/HES
Severity of illness (PIM-2/PIM-3 score and individual variables from first contact with transport team, not from referral)	PICANet
Ventilated at referral	PICANet
Previous admission to intensive care	PICANet/CMP
Volume of referring hospital	HES or RCPCH data
Interventions prior to arrival of the transport team	PICANet
Referral location (A&E, HDU, theatre, ward etc.)	PICANet
Distance from transport team to referring hospital	PICANet
Season (winter defined as Nov to Feb)	PICANet/CMP
In hours versus out of hours (to include evenings and weekends)	PICANet
Interventions conducted when retrieval team arrives	PICANet
Grade of team leader	PICANet

The second model which will investigate the care delivered en route by the transport team will select variables from the above table as appropriate.

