#### **Model 1: The impact on mortality due to timeliness of access to care in transported children**

Three time frames will be considered when investigating the outcome of mortality and timeliness of access to care:

- Time to arrival at bedside after acceptance (we will investigate this first)

- Time of referral to time of acceptance
- Time of referral to time of admission to PICU

A variable to represent timeliness of access to care will be included to indicate if the transport was made in the desired time frame (e.g. continuous time to arrival or dichotomised using any targets: <3 hours: yes/no) or in groupings of 30 mins (0-30 mins; 30-60 mins; 60-90 mins etc.). Other confounders will be identified and included (see Section 5.3.2). If reasons for delay want to be investigated then the PICANet free text comments fields will be interrogated.

Differences which may exist between the transport teams will be accounted for in all analyses of the primary outcome either via use of logistic mixed models (random effect term for transport team) or logistic models with robust standard errors to account for clustering within transport services. Both of these approaches will give very similar (although not identical) results in terms of the coefficients. The model fit will be assessed to see if consideration of transport team improves the model fit via use of the AIC. If differences between transport teams are of direct interest, a categorical term to indicate the transport team will also be included within the model.

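### The Model 1 confounder pool offers severity recorded when the team arrives, which is after or inside the delay being studied, and the SAP neither names the target effect nor plans a comparison without it

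*SAP*

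**What the plan says.** Model 1 (SAP Section 5.3.3) relates mortality to three time scales. The first is "Time to arrival at bedside after acceptance (we will investigate this first"); the others are "Time of referral to time of acceptance" and "Time of referral to time of admission to PICU".

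The candidate adjustment variables stand in one table in Section 5.3.2, headed "List of potential confounders for consideration in each of the models". It includes "Severity of illness (PIM-2/PIM-3 score and individual variables from first contact with transport team, not from referral") and "Interventions prior to arrival of the transport team". It also includes variables known when the child is referred, among them ventilation at referral, referral location, diagnosis and comorbidity.

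The table is not a fixed adjustment set: "This table provides a pool of variables which we will select from". Under Section 5.3.2, key confounders are chosen first. A DAG is then drawn for each research question, DAGitty is used to find the minimal model, and the Study Management Group approves the DAG before analysis. The DAG will be published.

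The SAP does reason about timing in one place. It gives as an example that "care provided by the retrieval team upon arrival will impact on the time to" PICU admission, but not on the other two time scales. It does not say the same of severity recorded on arrival. Section 5.3.5 names instrumental variables, missing-data assumptions and model assumptions as sensitivity analyses. It does not name a fit with and without first-contact severity.

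**The concern.** Objective 1.1 asks whether timeliness of access is associated with outcome. One obvious route is that the child deteriorates while waiting. A severity score taken when the team arrives then partly records the result of the wait. Holding it constant compares late and prompt transports among children who arrive at the same condition, which sets that part of the harm aside. Interventions before the team's arrival can build up over the same wait.

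The primary outcome is at stake, on the exposure to be studied first. An adjusted odds ratio near 1 could come from the adjustment and be read as evidence that delay does not matter.

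**Working it through.** **Timing.** The score and the three exposures, set side by side:

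| Exposure | Interval ends at | First-contact severity is recorded |
|---|---|---|
| Acceptance to bedside | team arrival | at or just after the end |
| Referral to acceptance | acceptance | after the end |
| Referral to PICU admission | admission | inside the interval |

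The score is pre-exposure in no row. It does precede much of the care studied in Model 2, so the timing suits that model better, but one list serves both.

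**Simple attenuation.** Assume a true odds ratio of 1.5 and a share m acting through condition at arrival. Neither figure is in the SAP. On the log scale the adjusted odds ratio is about exp[(1 − m) × ln 1.5], with ln 1.5 = 0.405:

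- m = 0: 1.5
- m = 0.5: exp(0.203) = 1.22
- m = 0.8: exp(0.081) = 1.08
- m = 1: exp(0) = 1.0

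**Simulation.** There were 1,000,000 transports per scenario, with 15% late and 7% mortality as in Section 4.2. All effect sizes are assumed. Referral severity S0 is standard normal. Lateness depends on S0 with log-odds slope b, where a negative b means that sicker children are reached faster. First-contact severity is S1 = S0 + γ × late + normal noise (SD 0.5). The log-odds of death are a constant + S1 + δ × late.

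| γ | b | δ | OR unadjusted | OR adjusted for S0 | OR adjusted for S1 |
|---|---|---|---|---|---|
| 0.6 | 0 | 0 | 1.70 | 1.77 | 0.99 |
| 0.6 | −0.5 | 0 | 1.12 | 1.82 | 1.01 |
| 0.3 | −0.5 | 0.3 | 1.10 | 1.77 | 1.33 |
| 0.6 | −0.5 | 0.2 | 1.32 | 2.15 | 1.21 |
| 0 | −0.5 | 0.6 | 1.11 | 1.81 | 1.82 |

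Adjusting for S1 instead of S0 removes everything when all harm runs through deterioration before arrival (first two rows), part when the harm is mixed, and nothing when delay leaves S1 unchanged (last row). Where sicker children are reached faster, leaving severity out altogether also pulls the odds ratio down, to between 1.10 and 1.32.

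**Power.** Section 4.2 claims adequate power for 7% against 4% with 2,250 late and 12,750 prompt transports, and gives no percentage. Take two-sided 5% (assumed) and 7% in the late group:

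- Pooled rate = (157.5 + 510)/15,000 = 0.0445.
- Null SE = √[0.0445 × 0.9555 × (1/2,250 + 1/12,750)] = 0.00472.
- Alternative SE = √(0.07 × 0.93/2,250 + 0.04 × 0.96/12,750) = 0.00565.
- z = (0.03 − 1.96 × 0.00472)/0.00565 = 3.67, so power is 99.99%.

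The claim is therefore supported for an unadjusted comparison. If adjustment blocks 25%, 50% or 75% of the 3 points over a 4% baseline, the remaining differences are 2.25, 1.5 and 0.75 points. Unadjusted power for these is about 99.3%, 88% and 39%.

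**The case against.** A reader might infer that the SAP commits Model 1 to this adjustment and that the adjustment removes the harm under study. The documents support neither. The table is a pool, and the DAG step, approved before analysis and published, is the right tool. If first-contact severity is drawn as a consequence of waiting, a total-effect adjustment set leaves it out. The remark on timing in Section 5.3.2 is given as an example, so its silence on severity does not prove an oversight. The loss depends on a mediated share that the SAP does not supply, and it can be nil.

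Two further points stand. First, severity control before the interval is not absent from the pool: ventilation at referral, referral location, diagnosis and comorbidity are there. Only the physiological score is confined to first contact. Second, that score also carries severity that predates the wait. If sicker children are reached faster, dropping it without a substitute can hide harm. It is also too simple to treat care by the team as merely post-exposure for referral-to-admission. By the SAP's own account such care influences that interval, so it may confound it.

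What the objection does not meet is that DAGitty follows the arrows it is given. The SAP selects key confounders before the DAG is drawn and lists this score among the candidates, with no statement of total or direct effect to settle how it should be drawn. The instrumental-variable analyses give a further look at a null result, but they are aimed at unmeasured confounding and do not replace a fit with and without the score.

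**Conclusion.** The concern holds in a limited form. The pool permits, and the SAP does not rule out, adjusting Model 1 for a possible mediator, and the reader would have no planned comparison to show what that did. The effect ranges from none to all of the delay effect, depending on how much acts through condition at arrival. The attenuated odds ratios and the power figures above rest on assumed effects and only illustrate that range.

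The estimates without and with first-contact severity should not be presented as bounds. Residual confounding by urgency and adjustment for a mediator can both push toward no harm. In the simulated scenarios with mediation, the unadjusted and the first-contact-adjusted odds ratios both fell below the value adjusted for referral severity. Which model should lead is open to argument; reporting both is not costly. A null in the severity-adjusted model alone should not be read as evidence that delay is harmless.

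**What to change.** 1. State in Section 5.3.3 that Model 1 targets the total effect of delay.
2. Mark the measurement time of every variable on each Model 1 DAG. For acceptance-to-bedside and referral-to-acceptance, draw first-contact severity and pre-arrival interventions as post-exposure. For referral-to-admission, show that severity is recorded inside the interval.
3. Report Model 1 with pre-interval variables only, subject to the DAG: age, sex, ethnicity, IMD, comorbidity, diagnosis, ventilation at referral, referral location, previous intensive care admission, hospital volume, season and in or out of hours. Add severity at referral if the data hold it; the SAP does not say whether they do.
4. Beside it, report a labelled model that adds first-contact severity and pre-arrival interventions. Describe the pair as two estimates, not as bounds, and state that a null in the second alone does not show that delay is harmless.

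The cost is some SAP wording and one extra model per exposure. The pre-interval model has thinner severity control, so confounding by urgency remains possible there, and the report should say so.
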